## 2 SYNOPSIS

**Protocol Number:**

FX-322-202

**Title:**

A Phase 2a, Prospective, Randomized, Double-Blind, Placebo-Controlled, Single and Repeat-Dose, Multicenter, Exploratory Efficacy Study of FX-322 Administered by Intratympanic Injection in Adults with Stable Sensorineural Hearing Loss

**Investigational Product:**

FX-322

**Study Centers:**

Approximately 15 centers in the US

**Phase:**

Phase 2a

**Objectives:****Primary Objective(s)**

1. To assess the exploratory efficacy by audiologic response following single and repeat doses of FX-322 in subjects with stable sensorineural hearing loss.
2. To assess the local and systemic safety of single and repeat doses at of FX-322 in subjects with stable sensorineural hearing loss.

**Endpoints:****Efficacy Endpoint(s)**

- Mean changes from Screening in:
  - Word Recognition in quiet (WR)
  - Words-In-Noise testing (WIN)
  - Standard Pure Tone Audiometry (air 0.25-8 kHz; bone 0.5-4 kHz)

**Additional Exploratory Efficacy Endpoint(s)**

- Mean changes from Screening in:
  - Extended High Frequency Audiometry (air 9-16 kHz)
  - Tinnitus Functional Index (TFI)
  - Hearing Handicap Inventory for Adults (HHIA)
  - Hearing Screening Inventory (HSI)

**Safety Endpoint(s)**

- Adverse events
- Changes from Screening in:
  - Otoscopy
  - Tympanometry

**Study Design:**

This is a Phase 2a, prospective, randomized, double-blind, placebo-controlled, single and repeat-dose, multicenter, exploratory efficacy study of FX-322, administered by intratympanic injection, in adults with stable sensorineural hearing loss (no changes in air conduction greater than 10 dB at a single frequency or greater than 5dB at two contiguous frequencies from the prior audiogram to the Screening audiogram).

The study will have 3 phases: Screening, Treatment, and Follow-up.

**Screening:** Can occur up to 30 days prior to study drug administration (Baseline/Treatment Day 1). All subjects will be screened to determine study eligibility. As part of recording the medical history of subjects, concurrent use of hearing aids during the study will be documented. All subjects will return for the Baseline visit and evaluated to ensure they continue to meet appropriate inclusion/exclusion criteria applicable at that visit.

**Baseline/Treatment:** Approximately 96 subjects are planned to be enrolled in this study. The subjects will be randomized to receive FX-322 or placebo according to the different treatment group schedules listed below:

| Group Dosing Schedule |                      |              |              |               |               |
|------------------------------|----------------------|--------------|--------------|---------------|---------------|
| Treatment Group       | # of Subjects | Day 1 | Day 8 | Day 15 | Day 21 |
| 1                            | 24                   | FX-322       | Placebo      | Placebo       | Placebo       |
| 2                            | 24                   | FX-322       | FX-322       | Placebo       | Placebo       |
| 3                            | 24                   | FX-322       | FX-322       | FX-322        | FX-322        |
| 4                            | 24                   | Placebo      | Placebo      | Placebo       | Placebo       |

Once a subject has been identified as meeting all inclusion/exclusion criteria, the qualifying ear with the worse hearing (ear with the worst Screening pure tone average) will be selected, unless a rationale exists to treat the other ear (e.g. the worse hearing ear does not meet the study criteria). The study treatment or placebo will be administered on Day 1, Day 8, Day 15, and Day 21. The placebo will be matched to FX-322 in consistency and color.

Each subject will be placed in the supine position. Topical anesthesia will be administered to the tympanic membrane. Under a microscope, a 25-gauge needle will be used to inject FX-322 or placebo into the middle ear at the junction of the posterior inferior and posterior superior quadrant with the needle tip directed towards the round window. The posterior superior quadrant should be avoided to prevent injury to the ossicles. After injection, the subject will continue to lie with the injected ear facing up for 10-15 minutes. The injections will be performed at an appropriate location designated by a Board-certified Otolaryngologist trained and experienced in performing intratympanic injections. Safety monitoring will include recording of adverse events (AEs), safety laboratory assessments, and monitoring of tympanometry and otoscopic exams.

**Follow up:** Subject will be required to return to clinic for safety, otologic, and audiologic assessments at Days 15, 60, 90, 150, and 210 after the initial injection. Subjects will be contacted by phone for safety assessments at Days 30, 120, and 180.

**Number of Subjects:**

Approximately 96 evaluable subjects

**Study Duration:**

Screening phase: up to 30 days before first study drug administration (Baseline Visit).

Treatment phase: 21 days (4 treatment visits 7 days apart)

Follow-up phase: 7 months from Baseline (Day 1).

**Study Population:**

Male and female adults (18 to 65 years inclusive), otherwise healthy with stable sensorineural hearing loss.

**Statistical Analysis:**

**Sample Size:** The sample size of approximately 24 subjects per group was considered adequate to explore the potential efficacy of FX-322 associated with various dosing schedules and was not based on formal statistical evaluation.

**Statistical Methods:** Descriptive summaries will be provided for patient disposition, demographic and baseline disease data. Summary statistics for efficacy endpoints will be provided for each randomized treatment group and timepoint. Comparisons of each FX-322 group to placebo along with 95% confidence intervals of the difference will also be calculated. Additionally, comparisons among the 3 FX-322 groups will also be conducted as well as a pooled FX-322 group comparison to placebo group. The Full Analysis Set defined as all randomized subjects exposed to at least one dose of study drug, will comprise the analysis set for the exploration of efficacy. Additional sensitivity analyses will be conducted using a Per Protocol Analysis Set. Subjects will be analysed by their randomized treatment group for both the Full Analysis and Per Protocol Analysis Set analyses.

The incidence of treatment-emergent adverse events will be presented by preferred term and body system using the Medical Dictionary for Regulatory Activities (MedDRA®).

Tabulations will be provided by seriousness, severity, and relationship to study drug.

Laboratory, tympanometry and otologic data will be presented as summary statistics at each timepoint as well as changes from baseline and/or shift tables. All subjects exposed to study drug will be included in the Safety Analysis Set and included in the safety analyses according to the actual treatment group regardless of the randomized assignment.

Details of the planned statistical analyses and methods will be provided in the Statistical Analysis Plan (SAP) which will be finalized prior to database lock and study blind break

PROTOCOL Version 5.0 Amendments

| Item No. | Change  | Section and Page Number(s)              |
|----------|---|---|
| 1        | Updated date and version of protocol.                                     | Title Page, pg.1
Footer, every page  |
| 2        | Updated language regarding data monitoring at the Day-90 Interim Analysis | Section 14.1.6 Interim Analysis pg. 41. |

PROTOCOL Version 4.0 Amendments

| Item No. | Change   | Section and Page Number(s)              |
|----------|--|---|
| 1        | Updated date and version of protocol.                                  | Title Page, pg.1
Footer, every page  |
| 2        | Updated information regarding blinding roles on the study              | Section 8.7.1 Blinding pg. 27.          |
| 3        | Updated language to conduct data monitoring following the Day 90 visit | Section 14.1.6 Interim Analysis pg. 41. |

PROTOCOL Version 3.0 Amendments

| Item No. | Change  | Section and Page Number(s)   |
|----------|---|--|
| 1        | Updated date and version of protocol.                       | Title Page, pg.1
Footer, every page   |
| 2        | Updated visit type from clinic to phone.                    | Synopsis, pg. 4
Section 8.1 Overall Study Design and Plan, pg. 17.
Section 8.1.2 Schedule of Assessments, pg. 18.
Section 10.1.4 – 10.1.9 Visits, pgs. 30-31. |
| 3        | Removed assessments from visits                             | Section 11 Efficacy Measures pg. 32.
Section 12.1.7 Otoscopy, pg 34.
Section 12.1.8 Tympanometry, pg 34.   |
| 4        | Updated language around interim analysis                    | Section 14.1.6 Interim Analysis pg. 41.  |
| 5        | Updated how missing data will be handled                    | Section 14.2 Handling of Missing Subject Data and Subject Withdrawals pg. 42.  |
| 6        | Updated text for grammatical and capitalization consistency | Throughout Protocol  |

PROTOCOL Version 2.0 Amendments

| Item No. | Change  | Section and Page Number(s)  |
|----------|---|---|
| 1        | Updated date and version of protocol.   | Title Page, pg.1
Footer, every page  |
| 2        | Added information and signature for Sponsor Chief Medical Officer                                 | Sponsor Signature, pg. 2  |
| 3        | Defined “ear with worst hearing” as ear with the worst Screening pure tone average                | Section 2 Synopsis, pg. 4
Section 8.1, Overall Study Design and Plan, pg. 15
Section 8.7.5, Selection and Timing of Dose for Each Subject, pg. 26 |
| 4        | Clarified randomization should be $\geq 50\%$ correct, $< 50\%$ correct for the WR scores         | Section 8.1 Overall Study Design and Plan, pg. 15
Section 8.7.3 Method of Assigning Subjects to Treatment Groups, pg. 25                             |
| 5        | Updated stability criteria for clarification  | Section 8.1 Overall Study Design and Plan, pg. 15
Section 8.4.2. Inclusion Criteria, pg. 19  |
| 6        | Updated Exclusion Criteria #4 to allow for clarification of definition of conductive hearing loss | Section 8.4.3. Exclusion Criteria, pg. 20   |
| 7        | Removed EMLA brand name to allow for use of generic topical anesthesia                            | Section 2 Synopsis, pg. 4
Section 8.5.1, Investigational Product Administered, pg. 22
Section 8.6.1 Packaging and Labeling, pg. 24                |
| 8        | Updated language to allow for subjects to be rescreened   | Section 8.4.5. Screen Failures, pg. 22  |
| 9        | Added guidance for which prior audiogram should be used to confirm Inclusion/Exclusion criteria   | Section 10.1.1 Screening, pg. 28  |
| 10       | Removed alcohol from urine drug testing   | Section 10.1.1 Screening, pg. 28
Section 12.1.2 Clinical Laboratory Evaluation, pg 33  |
| 11       | Clarified that the WR AESI should be recorded for the treated ear only                            | Section 13 Adverse Events, Adverse Events of Special Interest, pg. 36   |
| 12       | Updated descriptive statistics to reflect change in Inclusion Criteria                            | Section 14.1.1. Descriptive Statistics, pg. 37  |
| 13       | Updated text for grammatical and capitalization consistency                                       | Throughout Protocol   |

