### **8.6.1 Packaging and Labeling**

For the injection, the study drug or placebo will be provided in a kit with 4 study vials labelled for each injection (Injection 1, Injection 2, Injection 3, and Injection 4). The subject will be assigned just one kit for all of the study treatments. The [REDACTED] will be taken from general stock at the site. Topical anesthetic cream will be provided to the site. More information can be found in the Pharmacy Manual. The study drug and placebo will be prepared in a sterile 1 mL tuberculin syringe with a sterile cap. The syringe will be labelled clearly with the details for each randomized patient. Two syringes per patient will be provided in case a back-up syringe is needed for injection. The dose [REDACTED] will be filled to the [REDACTED] mark. The FX-322 and placebo preparations drawn into the syringes must be warmed in a heating unit. Refer to the Pharmacy Manual for further instructions.

The label(s) for the investigational product will include sponsor name, address and telephone number, the protocol number, investigational product name, dosage form, amount of investigational product per container, lot number, unique kit number, storage conditions, and required caution statements and/or regulatory statements, as applicable.

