#### **14.1.3 Analysis Sets**

- Full Analysis Set (FAS)

The Full Analysis Set is defined as all randomized subjects who receive at least one dose of study drug. Subjects will be analysed according to their randomized treatment group. The FAS will be used to explore efficacy. Details will be provided in the SAP.

- Per Protocol Analysis Set (PPAS)

The Per Protocol Analysis Set is defined as subjects receiving all four doses of study drug or placebo and without major protocol deviations that could interfere with interpretation of the results. These major protocol deviations will be identified prior to breaking the study blind. If different from the FAS, the PPAS may be used in additional sensitivity analyses. PPAS subjects will be analysed according to their randomized treatment group. Details will be provided in the SAP.

- Safety Analysis Set (SfAS)

The Safety Analysis Set will include all subjects exposed to study drug or placebo and will be analyzed according to the actual treatment group regardless of their randomized treatment assignment. The SfAS will be used for the analysis of safety. Both the treated and untreated ear will be included in the SfAS when the ear is the unit of the safety analysis.

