  - All tables that summarize results by treatment group for subjects in the Full Analysis Set (FAS) or Per Protocol Analysis Set (PPAS), defined in Section 4, will include each of the FX-322 treatment groups, a pooled FX-322 treatment group, and the placebo treatment group. Subjects in the FAS or PPAS will be classified into randomized treatment groups based on their randomized treatment.

Randomized Treatment Group	# of Subjects	Day 1	Day 8	Day 15	Day 21
FX-322 1x	24	FX-322	Placebo	Placebo	Placebo
FX-322 2x	24	FX-322	FX-322	Placebo	Placebo
FX-322 4x	24	FX-322	FX-322	FX-322	FX-322
FX-322 Pooled	72	FX-322	Placebo or FX-322	Placebo or FX-322	Placebo or FX-322
Placebo	24	Placebo	Placebo	Placebo	Placebo

- For assessments completed by ear for each subject, the unit of analysis will be the ear and treated and untreated ears will be summarized separately. Treated ears will be defined as the qualified ears for treatment that received at least one dose of study treatment per the randomized treatment schedule, and untreated ears will be the ears not qualified for treatment. For analyses by ear, the treatment group for each ear will be the subject’s randomized treatment group, regardless of actual administration in the given ear. All treated (qualified) ear data will be analyzed, including those with dosing administration errors. All untreated (not qualified) ear data will be analyzed up until any dosing administration error (wrong ear injection). For analyses by ear, data for untreated (not qualified) ears after a dosing administration error will be excluded from FAS and PPAS analyses.
- All tables that summarize results by treatment group for subjects in the Safety Analysis Set (SfAS) will include 1 FX-322 dose received, 2 FX-322 doses received, 4 FX-322 doses received, and placebo (0 FX-322 doses received). For SfAS analyses by subject, all subjects in the SfAS will be classified into actual treatment groups based on the actual number of FX-322 doses received in any ear (qualified or not qualified). In the event that any subject(s) receive 3 FX-322 doses, separate listings for subject(s) receiving 3 FX-322 doses will be created. Subjects receiving 3 FX-322 doses will be included in the total column.

Actual Treatment Group	# of Subjects Planned	Days 1-21
FX-322 1x	24	1 dose of FX-322
FX-322 2x	24	2 doses of FX-322
FX-322 4x	24	4 doses of FX-322
Placebo	24	0 doses of FX-322

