#### 4. ANALYSIS SAMPLES

The following definitions will be used to derive the analysis sets for this study.

- Full Analysis Set

The Full Analysis Set is defined as all randomized subjects who receive at least one dose of study drug (regardless of whether a full dose was administered) in the qualified ear per the

randomized treatment schedule. Subjects will be analyzed according to their randomized treatment group, as described in Section 3. For assessments completed by ear for each subject, treated (qualified) and untreated (not qualified) ears will be summarized separately, as described in Section 3. The FAS will be used to explore efficacy.

- Per Protocol Analysis Set

The Per Protocol Analysis Set is defined as subjects receiving all four doses of study drug or placebo in the qualified ear to be treated per the randomization treatment schedule and without major protocol deviations that could interfere with interpretation of the results. These major protocol deviations will be identified prior to breaking the study blind for the IA. Protocol deviations that occur after unblinding for the IA will be evaluated for major/minor classification by the blinded medical and study team prior to breaking the study blind for the CSR. If different from the FAS, the PPAS may be used in additional sensitivity analyses for efficacy. PPAS subjects will be analyzed according to their randomized treatment group, as described in Section 3. For assessments completed by ear for each subject, treated (qualified) and untreated (not qualified) ears will be summarized separately, as described in Section 3.

- Safety Analysis Set

The Safety Analysis Set will include all subjects exposed to study drug or placebo in any ear and will be analyzed according to the actual treatment group regardless of their randomized treatment assignment, as described in Section 3. For safety assessments by subject, the total number of FX-322 received in any ear will be used to assign actual treatment group. For safety assessments completed by ear for each subject, treated and untreated ears will be summarized separately, as described in Section 3. The SfAS will be used for the analysis of safety.

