## 11. CHANGES TO THE ANALYSES PLANNED IN THE PROTOCOL

Protocol Section 14.1.5 specifies that adjusted p-values and confidence intervals may be computed for pairwise treatment comparisons for a given endpoint. Such adjusted analyses are no longer planned in the SAP and there will be no adjustments for multiplicity of group comparisons.

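### The SAP narrows the protocol's Full Analysis Set to subjects with a qualified-ear dose per the randomised schedule, and Section 11 does not list the change

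*Protocol*

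**What the plan says.** **Protocol.** The synopsis gives the efficacy population as "The Full Analysis Set defined as all randomized subjects exposed to at least one dose of study drug". Section 14.1.3 repeats it: "The Full Analysis Set is defined as all randomized subjects who receive at least one dose of study drug". Neither sets a condition on which ear was injected or which product was given, and both analyse subjects by randomised group. Section 14.1.3 leaves details to the SAP.

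**SAP.** Section 4 admits randomised subjects "who receive at least one dose of study drug (regardless of whether a full dose was administered) in the qualified ear per the", and after a page break the sentence ends with the randomised treatment schedule. Section 3 carries the same condition into the ear-level analyses: "Treated ears will be defined as the qualified ears for treatment that received at least one dose of study treatment per the randomized treatment schedule". Section 3 also places each ear in its subject's randomised group whatever was actually given, and keeps treated-ear data affected by dosing errors. The PPAS in Section 4 separately requires all four doses in the qualified ear according to the schedule.

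**Disclosure.** SAP Section 11, on departures from the protocol, has one entry. It begins "Protocol Section 14.1.5 specifies that adjusted p-values and confidence intervals may be computed" and concerns multiplicity only. The version history for SAP 2.0 mentions the handling of treated and untreated ears for FAS and safety analyses, but does not say that FAS membership became narrower.

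**Kits.** Protocol 8.6.1 supplies four labelled vials per kit and states: "The subject will be assigned just one kit for all of the study treatments".

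**The concern.** Under the protocol, once a subject is randomised and injected, nothing that happens afterwards can remove that subject from the FAS. Under the SAP, membership also depends on where the injections went and, on one reading, on what they contained. That is a post-randomisation exclusion based on treatment received, placed in the set that serves the efficacy contrasts and the Day 90 interim efficacy tables.

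The exclusion reaches beyond the ear-level endpoints. TFI, HHIA and HSI are subject-level scores also analysed on the FAS (SAP 7.7 to 7.9), so a subject injected only in the wrong ear is lost from those as well. No planned efficacy analysis brings these subjects back: the extra summaries for wrong-ear dosing are descriptive and still restricted to FAS subjects, and the PPAS is stricter. SAP 8.2 tabulates incorrect treatment and wrong-ear dosing within the FAS, so the subjects with the most complete errors would be missing from the tables meant to show such errors.

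**Working it through.** The plan states no figure on this point. The check compares the definitions and then counts which dosing errors would remove a subject.

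**Inputs.** Schedules on Days 1, 8, 15 and 21 (Protocol 8.1; A = FX-322, P = placebo): 1x = A-P-P-P, 2x = A-A-P-P, 4x = A-A-A-A, placebo = P-P-P-P. There are 24 subjects per arm and 96 in total. Missed injections are not made up (Protocol 8.8.3).

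**Step 1: qualified-ear condition.** A subject injected only in the non-qualified ear meets the protocol definition and fails the SAP definition, in any arm and on any reading of the schedule phrase. A subject with at least one correct injection in the qualified ear stays in.

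**Step 2: schedule condition, read as product matching.** For each pair of arms, count the days on which the wrong kit supplies the randomised product. The count is the same in both directions, so six pairs cover all 12 combinations of randomised arm and kit given.

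| Swap | Matching days, all four injections given | Matches | In SAP FAS? |
|---|---|---|---|
| 1x / 2x | 1, 15, 21 | 3 | yes |
| 1x / 4x | 1 | 1 | yes |
| 1x / placebo | 8, 15, 21 | 3 | yes |
| 2x / 4x | 1, 8 | 2 | yes |
| 2x / placebo | 15, 21 | 2 | yes |
| 4x / placebo | none | 0 | no |

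With complete dosing, 2 of the 12 combinations remove the subject: 4x given a placebo kit, and placebo given a 4x kit. Under the protocol definition none does. So a 1x subject given a placebo kit stays in, while a 4x subject given the same kit is dropped.

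**Step 3: incomplete dosing under the same reading.**
- Stopped after Day 1: 1x/placebo, 2x/placebo and 4x/placebo swaps have no match.
- Stopped after Day 8: 2x/placebo and 4x/placebo have none.
- Stopped after Day 15, or all four given: only 4x/placebo has none.
- Swaps between two FX-322 arms can have no match only if the Day 1 injection was not given. That is remote, because randomisation and the first injection fall at the same visit (Protocol 10.1.2).

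Apart from kit swaps, the only reordering of a subject's own vials that leaves no match is a 2x kit used as P-P-A-A.

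**Step 4: size.** One excluded subject is 1/24 = 4.2% of an arm. One swapped 4x/placebo pair would leave 24 − 1 = 23 in each of those arms, 72 − 1 = 71 in pooled FX-322 and 96 − 2 = 94 overall. The documents give no error rate; 0 to 2 excluded subjects is an assumption.

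**The case against.** **The schedule phrase is ambiguous.** In SAP Section 4 it may describe only the qualified ear being dosed at the scheduled visits, with no test of the product given. Every wrong-kit subject injected in the qualified ear would then stay in, and Steps 2 and 3 would fall away. The as-randomised grouping in Section 3 and the FAS tables of incorrect treatment in 8.2 fit that reading. The treated-ear definition in Section 3 attaches the condition to the treatment received, which favours product matching, but the text does not settle it. The qualified-ear restriction stands either way.

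**The change is partly disclosed.** Protocol 14.1.3 defers details to the SAP, and the version history announces new handling of ears. That is fair, but an added membership condition changes the population, and Section 11 is where a reader would look for it.

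**Little rests on it.** The trial is exploratory, with no single primary endpoint, descriptive p-values and a sample size without formal basis. For wrong-ear dosing, every arm receives four blinded injections, so no arm-related mechanism is shown. This stands and limits the weight of the point.

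**SAP Section 3 might seem to contradict itself** by keeping ears with dosing errors while these subjects are dropped. It does not strictly do so: the rule covers ears that already meet the treated-ear definition. The two provisions are in tension only.

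**Conclusion.** The discrepancy is real and undeclared in Section 11. Subjects never dosed in the qualified ear lose their place in the FAS, in any arm. Subjects with no matching dose lose theirs only if the schedule phrase means product matching. The effect is probably small: nothing at zero such errors, and 4.2% of an arm per excluded subject under the assumed range of 0 to 2. No effect on any estimate has been shown.

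Three stronger inferences are not supported:
- That dosing errors in general remove subjects. Partial errors remove nobody, and 10 of the 12 whole-kit swaps with complete dosing remove nobody.
- That the loss is confined to 4x versus placebo. That holds only for whole-kit swaps with all four injections given, and only under product matching; wrong-ear exclusions can fall in any arm.
- That the SAP expects such errors. Its wording is conditional: it provides for them without saying how many will occur. Nor do the documents report or anticipate a whole-kit swap.

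**What to change.** In SAP Section 4, restore the protocol definition: all randomised subjects who receive at least one dose of FX-322 or placebo, analysed by randomised group, with ear-level endpoints taken on the qualified ear. In SAP Section 3, define the treated ear for FAS tables as the qualified ear of an FAS subject, with a footnote for any qualified ear that was never injected. Leave the correct-ear and correct-schedule conditions to the PPAS, which already has them.

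If the sponsor prefers the narrower set, Section 4 should say whether the schedule phrase refers to the ear or to the product, Section 11 should list and justify the change, and an efficacy analysis of all randomised and dosed subjects should be added.

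Restoring the protocol definition costs SAP wording only. The downside is slight dilution of the FAS contrasts by mis-dosed subjects, as in any as-randomised analysis. The planned PPAS repeats show the result without them for word recognition, words-in-noise and audiometry, but not for the questionnaires, for which SAP 7.7 to 7.9 plan no sensitivity analyses.
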